6.5.2 Long Term Adverse Events

All Bone fracture and bone events occurred after patients entering long-term follow up period will be summarized by NCI-CTCAE toxicity criteria. Same summary will also be provided for serious bone fracture and bone events during long-term follow up period. A listing of bone fracture and bone events will be provided for entire study period and during follow-up period, respectively.

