HEOR	Health Economics, Outcomes & Reimbursement
IBW	Ideal Body Weight
ICH	International Committee on Harmonization
ID	Identifier
INN	International Non-proprietary Name
ITT	Intent-to-treat
IV	Intravenous

IVRS/IWRS	Interactive voice/web response system
IXRS	Interactive response system (independent of type)
JSRC	Joint Safety Review Committee
kBq	Kilobecquerel
LCL	Lower Confidence Limit
LTFU	Long-Term Follow-Up
LTFUAE	Long-Term Follow-Up Adverse Event
MedDRA	Medical Dictionary for Regulatory Activities
MRI	Magnetic resonance imaging
NCI	National Cancer Institute
NCCN	National Comprehensive Cancer Network
NIS	Non-interventional Study
NIST	National Institute of Standards and Technology
nMiss	Number of missing values
OS	Overall survival
PC	Prostate cancer
mPCWG2	Modified Prostate Cancer Working Group 2
PRO	Patient Reported Outcomes
PSA	Prostate specific antigen
PT	Preferred Term
QoL	Quality of Life
Ra-223	Radium-223 dichloride
rPFS	Radiological progression free survival
SAE	Serious Adverse Event
SAF	Safety
SAP	Statistical Analysis Plan
SD	Standard Deviation
SMQ	Standardized MedDRA Queries
SOC	System Organ Class
SOP	Standard Operating Procedure
SSE	Symptomatic skeletal event
SSE-FS	Symptomatic skeletal event free survival
Std	Standard Deviation
TAS	(Bayer) Therapeutic Area (Oncology) Standards
TBW	Total Body Weight
TEAE	Treatment-Emergent Adverse Event
TTP	Time to progression
uCi	Microcurie
UCL	Upper Confidence Limit
W12	Week 12
W24	Week 24
WHO	World Health Organization
WHO-DD	World Health Organization Drug Dictionary

1. Introduction

Protocol 16507 is a 3-arm, randomized, open-label Phase II study to compare the efficacy and safety of a “standard dose” regimen of radium-223 dichloride with, a “high dose” regimen and an “extended dose” regimen, in subjects with castration-resistant prostate cancer metastatic to bone .

The study's 3 arms are:

- Arm A: 6 doses of 50 kBq/kg (55 kBq/kg after implementation of NIST update) radium-223 dichloride every 4 weeks ("standard" dose regimen)
- Arm B: 6 doses of 80 kBq/kg (88 kBq/kg after implementation of NIST update) radium-223 dichloride every 4 weeks ("high dose" regimen)
- Arm C: 12 doses of 50 kBq/kg (55 kBq/kg after implementation of NIST update) radium-223 dichloride every 4 weeks ("extended dose" regimen)

The study's co-primary endpoints are:

- Symptomatic skeletal event free survival from randomization (SSE-FS1) for the "standard dose" vs. "high dose" comparison (Comparison 1).

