- Symptomatic skeletal event free survival from the 6th dose (SSE-FS2) for the "standard dose" vs. "extended dose" comparison (Comparison 2)

Two analyses of efficacy and safety are planned in this study:

- A final analysis to occur after the latest of the following maturation criteria are met:
 - 135 SSE-FS (SSE-FS1) events in subjects included in Comparison 1
 - 75 SSE-FS (SSE-FS2) events following the 6th dose in subjects included in Comparison 2
 - The last subject has been followed for 30 days from last treatment.
- An updated analysis to occur after the last subject has completed the active follow-up period in this study for two years following last dose of Ra-223 dichloride (if after primary endpoint cut-off).

Additional details on the timing of the analyses are described in Section 3.3 below.

This Statistical Analysis Plan (SAP) specifies the analyses and data presentations planned for both the final and the updated analysis.

This SAP was written based on the following documentation:

Document	Date	Version
Protocol	9 August 2013	1.0
Protocol Amendment no. 1	20 November 2013	2.0
Protocol Amendment no. 2	16 August 2015	3.0
Protocol Amendment no. 3	16 May 2017	4.0

2. Study Objectives

Co-primary objectives:

- To evaluate efficacy as measured by SSE-FS of radium-223 dichloride 50 kBq/kg (55 kBq/kg after implementation of NIST update) every 28 days for up to 6 doses

compared to radium-223 dichloride 80 kBq/kg (88 kBq/kg after implementation of NIST update); and

- To evaluate efficacy as measured by SSE-FS of radium-223 dichloride 50 kBq/kg (55 kBq/kg after implementation of NIST update) every 28 days for up to 6 additional doses compared to no further radium-223 dichloride treatment in subjects with CRPC metastatic to the bone who previously received radium-223 dichloride 50 kBq/kg (55 kBq/kg after implementation of NIST update) every 28 days for up to 6 doses, and survived SSE free and are eligible for further radium-223 dichloride treatment.

Symptomatic skeletal events (SSEs) are defined as:

- The use of external beam radiotherapy (EBRT) to relieve skeletal symptoms
- New symptomatic pathological bone fractures (vertebral and non-vertebral)
- Tumor-related orthopedic surgical intervention
- Spinal cord compression

Secondary objectives:

- To evaluate safety and tolerability
- To evaluate overall survival (OS)
- To evaluate pain improvement rate
- To evaluate time to pain progression
- To evaluate time to first SSE

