3.1 Study periods and duration

The study periods will consist of screening/randomization, treatment, active follow-up with clinic visits, active follow-up without clinic visits, and long-term follow-up.

Long-term follow-up:

All study subjects will be eligible for further follow-up either in this study or in a separate long-term follow-up study for up to 7 years.

Transition of all subjects into the separate long-term follow-up study will begin following the later of primary endpoint completion or 2 years after the last radium-223 dichloride treatment is administered to the last treated subject.

Until the transition to the long term follow-up study begins, some subjects may begin long-term follow-up in this study. This study will end when all subjects have transitioned into the long-term follow-up study or discontinued from this study for another reason (e.g., Consent Withdrawn, Lost to Follow up).

Data collected in the separate long-term follow-up study is outside the scope of this SAP.

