6.4 Safety

No formal statistical tests will be done for the safety endpoints.

A safety analysis will be performed at the same time as the final primary endpoint analysis. This analysis will include treatment-emergent safety events as of database closure for primary endpoint completion.

An updated analysis of safety events will be performed after the last followed patient completes active follow-up 2 years following the last dose of radium-223 dichloride treatment, which will be reported in a separate document from the Clinical Study report. In addition, safety events emerging during long-term follow-up conducted as part of this study will be reported in separate document(s) from the study Clinical Study Report.

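### Long-term follow-up fractures are summarised by CTCAE grade with no allowance for observation time, although 12-dose Arm C completers enter that period 24 weeks later than 6-dose completers

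*SAP*

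**What the plan says.** Supplemental SAP v2.0, section 6.5.2: "All Bone fracture and bone events occurred after patients entering long-term follow up period will be summarized by NCI-CTCAE toxicity criteria". The same summary is planned for serious events, with listings for the whole study and for follow-up. The section does not mention time at risk and does not say whether the table is split by arm. The main SAP, section 6.4.1, had kept long-term follow-up adverse events to listings. Time to fracture (Supplemental SAP v2.0, section 6.5.1) is a Kaplan-Meier analysis by arm, but fracture-free subjects are censored at the end-of-treatment visit or at their last visit before active follow-up.

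The timing comes from the main SAP:

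- Section 3.1 gives the order of the later periods: "active follow-up with clinic visits, active follow-up without clinic visits, and long-term follow-up".
- Section 1 ties the updated analysis to completion of the "active follow-up period in this study for two years following last dose of Ra-223 dichloride". Section 6.4 places the updated safety analysis "after the last followed patient completes active follow-up 2 years following the last dose of radium-223 dichloride treatment".
- Section 3.1 starts the move to the separate study at the "later of primary endpoint completion or 2 years after the last radium-223 dichloride treatment is administered to the last treated subject". Before that, "Until the transition to the long term follow-up study begins, some subjects may begin long-term follow-up in this study".
- Section 1 gives the dosing: "Arm A: 6 doses of 50 kBq/kg (55 kBq/kg after implementation of NIST update) radium-223 dichloride every 4 weeks". Arm B has the same number and spacing of doses, and Arm C has 12 at the same spacing.

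**The concern.** Entry to long-term follow-up is tied to each subject's last dose, while the point at which it starts to close is a calendar date shared by all. The arm with the longer course therefore starts later and meets the same closing point. A table of subjects with a fracture by grade takes no account of this. If arms are set side by side, the extended regimen would tend to show fewer late fractures than the other two even if the fracture hazard were the same. No other planned fracture safety analysis covers this period with an allowance for time. The supplement adds fracture analyses specifically, so this table is likely to be read as evidence on bone safety.

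**Working it through.** **Inputs (main SAP, sections 1, 3.1, 3.4 and 6.4).** Enrolment is 30 per month after a 7-month ramp-up, lasting about 16 months, for 360 subjects. The last treatment is 44 weeks (10.12 months) after the last accrual. The primary cut-off is expected at 39.1 months. Active follow-up lasts two years from last dose. First dose is taken to be at enrolment, with no dose delays.

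**Plan's own figures first.** A simulation of the design (1,500 replicates) gives a mean cut-off of 39.1 months with a linear ramp, 39.3 with a stepped ramp and 38.0 with uniform accrual, against 39.1 stated. It gives about 186 and 74.7 events against 186.61 and 74.91, and 55.2–55.4% eligible at 24 weeks against 55.35%. Power for Comparison 1 is 0.904–0.917 against 0.905. For Comparison 2 it is 0.776–0.800, slightly below the stated 0.806. The timeline is reproduced well enough to use.

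**Gap at entry.** Dose 6 falls at week 20 (20/4.348 = 4.60 months) and dose 12 at week 44 (44/4.348 = 10.12 months). The difference is 24 weeks, or 5.52 months.

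**Start of closure.** 16 + 10.12 + 24 = 50.1 months, later than 39.1, so the limb counted from the last treatment governs.

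**Window for a completer enrolled at month u.** Closure − (u + last dose + 24). For Arm C this reduces to last accrual − u. For Arms A and B it is 5.52 months longer.

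- Linear ramp over the full 16 months: mean u = (105 × 4.667 + 270 × 11.5)/375 = 9.59. Arm C: 16 − 9.59 = 6.4 months. Arms A/B: 6.4 + 5.5 = 11.9 months. Ratio 0.54.
- The same ramp stopped at 360 subjects (month 15.5): mean u = (105 × 4.667 + 255 × 11.25)/360 = 9.33. Arm C: 6.2 months. Arms A/B: 11.7 months. Ratio 0.53.
- The last subject enrolled, if a completer, has 5.5 months in Arms A/B and none in Arm C.

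**Sensitivity.** The SAP fixes none of the departures below, so they are assumptions. Each is varied on its own; *ramp* is the linear ramp stopped at 360 subjects.

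| Scenario | Arms A/B (months) | Arm C (months) | Ratio |
|---|---|---|---|
| Ramp, closure at start of transition | 11.7 | 6.2 | 0.53 |
| Uniform 16-month accrual | 13.5 | 8.0 | 0.59 |
| Closure 6 months later (ramp / uniform) | 17.7 / 19.5 | 12.2 / 14.0 | 0.69 / 0.72 |
| Closure 12 months later (ramp / uniform) | 23.7 / 25.5 | 18.2 / 20.0 | 0.77 / 0.78 |
| Uniform accrual over 24 months | 17.5 | 12.0 | 0.68 |
| Uniform accrual over 30 months | 20.5 | 15.0 | 0.73 |
| Deaths in the period, median 24 to 10 months (ramp) | 9.8 to 7.8 | 5.5 to 4.7 | 0.56 to 0.60 |
| The same, uniform accrual | 11.0 to 8.5 | 6.9 to 5.7 | 0.63 to 0.67 |
| All of Arm C, half of entrants completers, rest timed as A/B (ramp) | 11.7 | 8.9 | 0.76 |

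Stacking assumptions moves the ratio further. Uniform accrual, closure 12 months late and a 10-month median survival together give 0.90. Every scenario run stays below 1.

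**Effect on a crude table.** Assume an equal fracture hazard of 10% per year and the windows of 11.9 and 6.4 months. Arms A/B: 1 − exp(−0.1 × 11.9/12) = 9.4%. Arm C completers: 1 − exp(−0.1 × 6.4/12) = 5.2%. The ratio is 0.55. If only half of Arm C's entrants are completers, the arm figure is about (9.4 + 5.2)/2 = 7.3%.

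**The case against.** The strongest reply is that the harm depends on text that is not there. Section 6.5.2 does not say that the table is by arm, whereas the supplement does say so in sections 6.1.1 and 6.5.1. Nor does it say that only counts will be shown. This stands as a limit: both are fair readings, supported by the by-arm reporting of treatment-emergent events in the main SAP, section 6.4.1, but they remain readings.

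The two-year entry point is also not stated as a rule. It is inferred from sections 1, 3.1 and 6.4, which agree with one another; the protocol may define it directly.

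A reader might infer that Arm C as a whole has half the observation time. The documents do not support that. Subjects who stop at or before dose 6 have no delay, those who stop between doses 7 and 11 have a shorter one, and section 3.4 expects only 55.35% of Arms A and C to be event-free and eligible at 24 weeks. Section 3.1 also says only that transition begins at the stated point, so in-study follow-up may run beyond it.

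A reader might further infer that a late bone-safety signal would be hidden. That goes too far. Safety is descriptive, fractures are listed individually, numbers entering long-term follow-up are shown by treatment group, and follow-up may continue in the separate study.

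None of this supplies an observation-time measure for the table.

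**Conclusion.** The point holds as a modest improvement to a descriptive safety table. The firm part is the 24-week (5.5-month) later entry for undelayed 12-dose completers against a shared calendar point, given the inferred two-year entry rule, and the absence of any allowance for it in section 6.5.2. About 6 versus 12 months (ratio 0.5 to 0.6) applies to completers under the planned accrual with closure at the start of transition. Slower accrual, later closure, or taking Arm C as a whole moves the ratio to roughly 0.7 to 0.8. If the table is shown by arm, crude proportions would tend to favour Arm C at equal hazard. The primary and secondary efficacy analyses are not affected.

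**What to change.** In Supplemental SAP v2.0, section 6.5.2, state that the table is by arm and report for each arm:

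- the number of subjects entering in-study long-term follow-up;
- the patient-years observed in it;
- fractures and serious fractures per patient-year, with confidence intervals.

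State the rule for entry to and exit from the period, so that person-time is defined.

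Add cumulative incidence from first dose only if fractures were collected regardless of relatedness during active follow-up. The main SAP, section 6.4.1, says the intention is to collect only treatment-related adverse events after the treatment period, so ascertainment between end of treatment and long-term follow-up may be incomplete.

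The cost is small: the person-time needs entry and last-contact dates, which should be confirmed as available. Few events will give wide intervals. The rates will still describe subjects who survived to enter the period, at different times since first dose, so they correct for unequal observation time but not for that selection.

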6.5.3 Long Term Safety

All Safety data arising during the long-term safety follow-up period in this study will be presented through listings.

7. Document history and changes in the planned statistical analysis

- Main SAP v2.0 dated 17 MAY 2017.
- SAP supplement v1.0 dated 02JUN 2018

8. References

Refer to the main SAP v2.0 dated 17 MAY 2017.
